## DESCRIPTION OF STUDY

### A. Purpose

1. To determine if ventral surgery is more cost-effective compared to dorsal (fusion or laminoplasty) surgery.
2. To determine the relative cost-effectiveness between anterior cervical discectomy and fusion (ACDF), posterior cervical fusion (PCF), and cervical laminoplasty.

### A. Background

This study aims to compare the cost of care of anterior versus posterior surgical approaches for the management of Cervical Spondylotic Myelopathy (CSM). Due to the significant gap in today's literature, we aim to conduct a post hoc analysis of data from the randomized trial "Cervical Spondylotic Myelopathy Surgical Trial" ([www.ClinicalTrials.gov](http://www.ClinicalTrials.gov); identifier: NCT02076113; LCID# 2013-085) to determine the cost effectiveness of various procedures as related to the management of CSM. Specifically, we aim to compare 1) the cost effectiveness of ventral surgery versus dorsal (fusion or laminoplasty) surgery; and 2) to determine the relative cost-effectiveness between anterior cervical discectomy with fusion (ACDF), posterior cervical fusion (PCF), and cervical laminoplasty.

The aforementioned study that the proposed analysis is based on was conducted in collaboration between multiple academic institutions in North America. The resulting clinical and patient-reported outcomes from the CSM-S RCT suggested similar effectiveness in both anterior and posterior surgical approaches. Of note, the study showed that cervical laminoplasty, a relatively low instrumentation-related cost procedure, was effective in managing CSM. The findings of the proposed analysis will offer further consideration on patient financial burdens as related to CSM management to better improve related clinical decision-making for both patients and their providers.

### B. Specific Location of Study

This is a post hoc analysis of data from a multicenter randomized clinical trial entitled "Cervical Spondylotic Myelopathy Surgical Trial" ([www.ClinicalTrials.gov](http://www.ClinicalTrials.gov); identifier: NCT02076113), which took place in eleven institutions across North America. Data will be analyzed by Mayo Clinic statisticians specializing in cost analyses.

### C. Duration of Project

Statistical analysis and manuscript writing is expected to be completed within a 12-month period.

### D. Research Plan

1. Post hoc analysis will be conducted on the following data that were collected during the trial (LCID#2013-085) The study flow schema is outlined in Figure 1
  1. Our post hoc study will utilize the health resource information, well-known quantitative scales to measure functional outcomes (SF-36, Oswestry Neck, mJOA, and EuroQol-5D taken at pre-op, 3 months, 6 months, 1 year, 2 years, 3 years, 4 years, and 5 years), costs related and incidence of re-operations and complications at 30 days and 1 year after surgery to compare the costs related to each procedure: comparing the cost effectiveness of ventral surgery versus dorsal (fusion or laminoplasty) surgery and comparing the relative cost-effectiveness between anterior cervical discectomy with fusion (ACDF), posterior cervical fusion (PCF), and cervical laminoplasty. Quality of life measures (I.e. SF-36 as one overall score per timepoint) will be utilized to determine patient satisfaction with the procedure of choice and subsequently create a comprehensive snapshot for clinical decision making. Utilization of quality-of-life scales will help relate success of the procedure as deemed by the patient in relation to the related costs.
  2. Health resource utilization information was collected using patient diaries along with copies of all medical bills and receipts at 1 month, 3 months, 6 months, and 12 months post-operatively for all patients. Participants were asked to monitor days missed from work and days unable to perform usual activities, in addition to days missed from work for medical treatments or evaluations.
2. The overall cost will be estimated for each patient from a societal perspective and will include the following components:
  - I. *Index Hospitalization Cost – performed on all patients:*
    - Hospital Costs: Total hospital charges (Total HC) will be used to estimate costs using hospital-specific and year-specific Medicare cost-to-charge ratios (CCR). The costs will be adjusted for inflation to the latest year of the study (2018) without a 3% discount. – *Assumptions:* cost-to-charge ratios for all hospitals and all relevant years will be provided. Data will be complete for all patients from all sites.
    - Hospital charges for specific revenue centers (i.e., radiology, pharmacy, physiotherapy, and occupational therapy) will be converted to costs using hospital-specific and year-specific CCRs. This will allow the identification of the major drivers of the difference in cost between the surgical strategies. A crosswalk between the revenue center and the cost center will have to be created. – *Assumptions:* Total hospital charges will be segmented out into the relevant revenue centers. All patients will have charges segmented in this manner. No major differences in how total hospital charges will be segmented by each site will exist.
    - For professional services (identified with either HCPCS code or CPT-4 codes) provided to patients during the index hospitalization, costs will be calculated using national reimbursement amounts from the appropriate Medicare fee schedules for the respective year. – *Assumptions:* Detailed line-item services of all HCPCS codes and CPT-4 codes (including any necessary billing modifiers) will be provided for all professional services. Data will be complete for all patients from all sites.

- II. *One-year All-Cause Cost – performed on patients from sites capturing 1 year utilization:*
  - One-year all-cause costs will be calculated for hospital and professional services in the manner described above. – *Assumptions:* The same underlying assumptions described above.
  
- III. *Time to Return to Work – performed on all patients reporting employment:*
  - We will assume that the work halted for patients on the procedure date).
  - For patients to whom this outcome applies, we will compare different cohorts using return to work as a time-to-event outcome.
    - Lost wages will be estimated using the median weekly earnings in the US as reported by the Bureau of Labor Statistics.
      - Patients providing no employment information will be assumed to have zero lost wages.
      - Job-specific wages will not be estimated.
  
- IV. Index hospitalization costs and one-year all-cause costs will be combined with costs due to loss of productivity (indirect costs) to estimate total costs for each patient from a societal perspective.

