#### F. Timepoints of Data Collection

[figure not shown]
1. Data variables included in the analysis:
  - I. Procedure costs and related costs; related CPT codes
  - II. SF-36 (pre-op, 3 months, 6 months, and 1 years)
  - III. EQ5D (pre-op, 3 months, 6 months, and 1 years)
  - IV. Neck pain disability index (pre-op, 3 months, 6 months, and 1 years)
  - V. Baseline Demographics
  - VI. MJOA (pre-op, 3 months, 6 months, and 1 years)
  - VII. Return to Work Status 1 Month, 3 Months, 6 Months, 1 Year
  - VIII. Health Resource Utilization Diary (1 month, 3 months, 6 months, 1 year)
  - IX. Inpatient Hospital and Rehabilitation Utilization Data
  - X. Hospital-specific and year-specific Medicare cost-to-charge ratios
  
2. Study Endpoints
  - I. The primary endpoint will be the cost-effectiveness comparison between ventral and dorsal surgery in CSM.

II. The secondary endpoint will be the cost-effectiveness comparison between dorsal cervical fusion and laminoplasty

[figure not shown]
3. Data Timepoints

- I. Preop: SF36, EQ5D, neck pain disability index
- II. Procedure: related hospital costs, hospital-specific and year-specific Medicare cost-to-charge ratio
- III. 1 month: Complications and related costs (if applicable), health resource utilization diary, Return to Work Status
- IV. 3 months: SF36, EQ5D, neck pain disability index, health resource utilization diary, Return to Work Status
- V. 6 months: SF36, EQ5D, neck pain disability index, health resource utilization diary, Return to Work Status
- VI. 1 year: SF36, EQ5D, neck pain disability index, health resource utilization diary, Return to Work Status

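### Pricing hospital cost from total charges with one ratio per hospital and year may misprice fusion and laminoplasty unequally, and the planned center-level step omits implants and operating room

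*Protocol*

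**What the plan says.** Section D, item 2.I (Index Hospitalization Cost) describes two conversions of hospital charges.

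- The first bullet gives the hospital cost: "Total hospital charges (Total HC) will be used to estimate costs using hospital-specific and year-specific Medicare cost-to-charge ratios (CCR"). The ratio is indexed by hospital and by year. No cost-center index is mentioned, and the quantity converted is the total charge.
- The second bullet converts parts of the bill: "Hospital charges for specific revenue centers (i.e., radiology, pharmacy, physiotherapy, and occupational therapy) will be converted to costs using hospital-specific and year-specific CCRs". Its stated use is this: "This will allow the identification of the major drivers of the difference in cost between the surgical strategies". It adds: "A crosswalk between the revenue center and the cost center will have to be created". Its assumptions include: "Total hospital charges will be segmented out into the relevant revenue centers. All patients will have charges segmented in this manner".

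Nothing in item 2.I says that the center-level costs are added up to form the hospital cost. Item 2.II applies the same approach to one-year costs, and item 2.IV carries both into the societal total.

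The Background states that "cervical laminoplasty, a relatively low instrumentation-related cost procedure, was effective in managing CSM". Section F, under Study Endpoints, states: "The secondary endpoint will be the cost-effectiveness comparison between dorsal cervical fusion and laminoplasty". The primary endpoint there is the comparison of ventral with dorsal surgery, and section A (Purpose) defines dorsal as fusion or laminoplasty.

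**The concern.** Applying one ratio to a total bill treats implants, operating room time, ward care and pharmacy as if all were marked up equally over cost. For a comparison of procedures this does no harm if the procedures have the same mix of charges, or if the ratios really are equal. The Background indicates that the mix is not the same, because it singles out laminoplasty for its low instrumentation cost. Any gap between the implant ratio and the overall ratio is then multiplied by the difference in implant charges and passes directly into the incremental cost.

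The protocol itself treats center-level ratios as relevant, since a crosswalk from revenue centers to cost centers has little purpose if every center gets the same ratio. Yet that step serves only to explain drivers. As listed, it also misses the components most likely to separate the procedures, namely implants/supplies and operating room.

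At stake is the numerator of the cost-effectiveness comparison. The Background reports similar effectiveness for the anterior and posterior approaches, so the cost difference will carry much of the conclusion.

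**Working it through.** The protocol gives no charge, cost-to-charge ratio or implant price, so there is no figure of its own to reproduce. The check is an identity evaluated over assumed values.

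**Formula.** Let *k* be the single hospital-year ratio, *k_impl* and *k_rest* the center-level ratios for implants and for everything else, and *C* the charges, with F for fusion and L for laminoplasty. The error in the fusion-minus-laminoplasty cost difference from using the single ratio is

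(C_impl,F − C_impl,L)(k − k_impl) + (C_rest,F − C_rest,L)(k − k_rest).

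**Inputs (all assumed).** Non-implant charges are $60,000 for both procedures. Implant charges are $40,000 for fusion and $10,000 for laminoplasty, a gap of $30,000. The ratios are k = k_rest = 0.30, which makes the second term zero and isolates the implant effect. The implant ratio varies from 0.20 to 0.50.

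**Single ratio.** Fusion: 0.30 × 100,000 = $30,000. Laminoplasty: 0.30 × 70,000 = $21,000. Difference: $9,000.

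**Center-level ratios.** Fusion: 0.30 × 60,000 + k_impl × 40,000. Laminoplasty: 0.30 × 60,000 + k_impl × 10,000.

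| k_impl | Fusion | Laminoplasty | Difference | Error of single ratio in the difference | Error in fusion cost | Error in laminoplasty cost |
|---|---|---|---|---|---|---|
| 0.20 | $26,000 | $20,000 | $6,000 | +$3,000 | +15.4% | +5.0% |
| 0.30 | $30,000 | $21,000 | $9,000 | $0 | 0% | 0% |
| 0.40 | $34,000 | $22,000 | $12,000 | -$3,000 | -11.8% | -4.5% |
| 0.50 | $38,000 | $23,000 | $15,000 | -$6,000 | -21.1% | -8.7% |

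The first term of the identity gives the same errors: 30,000 × (0.30 − 0.20) = +3,000 and 30,000 × (0.30 − 0.50) = −6,000.

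**Smaller gap.** With implant charges of $25,000 and $10,000, the single ratio gives 0.30 × 15,000 = $4,500. Center-level ratios give 0.20 × 15,000 = $3,000 up to 0.50 × 15,000 = $7,500, so the error runs from +$1,500 to -$3,000.

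**What follows.** The error is proportional to the implant-charge gap and to the gap between the ratios. It can take either sign and vanishes when the ratios coincide.

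**The case against.** The case for the plan as written has real force.

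- **The single ratio is a reading.** The protocol does not call the ratio hospital-wide and does not name a base case. It uses almost the same phrase for the ratios in the revenue-center step, so the phrase alone does not exclude center-level ratios, and an SAP could settle the matter. This stands as a limit on certainty. Still, the first bullet converts the total charge and the second confines center-level work to finding drivers, so one ratio per hospital-year remains the natural reading.
- **A breakdown beside a total is no contradiction.** A reader might infer that the two bullets cost the same charges in incompatible ways. The text does not support that. It never says the four centers should sum to the total, and if both steps used the same ratio they would agree. They diverge only if the ratios differ by center.
- **The listed centers do not reach implants.** A reader might infer that the planned step already supplies what is needed. It does not, because implants/supplies and operating room are not among the four centers. The assumption that total charges are segmented makes an extension feasible. It does not guarantee that every hospital and year has a matched implant ratio.
- **Total-charge costing needs fewer assumptions.** Center-level costing relies on the protocol's assumption that sites segment their bills alike, across eleven institutions. Total-charge costing does not. This is a fair argument for keeping it in the analysis, and for not mixing the two methods between sites.

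**Conclusion.** The concern holds in conditional form. As most naturally read, the hospital cost entering the total rests on one ratio per hospital and year. The center-level step is limited to identifying drivers and omits the centers where instrumentation would appear. Fusion and laminoplasty may therefore be priced with unequal error.

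A reader might go further and infer that the two procedures are mispriced, or that the plan favors one of them. The protocol does not support that: without charges or ratios, neither direction nor size can be derived. The range of +$3,000 to -$6,000 rests wholly on the assumed $30,000 gap, the overall ratio of 0.30 and implant ratios from 0.20 to 0.50.

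The exposure is clearest for the secondary endpoint, because the only documented contrast in instrumentation concerns laminoplasty. It is less certain for ventral versus dorsal, where the dorsal group combines fusion and laminoplasty and no implant-charge gap is documented. The point should be addressed, but it does not show the planned total to be wrong.

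**What to change.** 1. State which level of ratio is applied to total charges.
2. Extend the planned crosswalk to all revenue centers, naming implants/supplies and operating room explicitly.
3. Compute hospital cost as the sum over centers of the center's charge times the matched cost-center ratio for that hospital and year. Report it alongside total charges times the hospital-year ratio.
4. Choose one method for the main analysis and apply it uniformly across sites: center-level if all sites can segment their charges, total-charge otherwise. Prespecify the other as a sensitivity analysis.
5. Apply the same rule to the one-year hospital costs, which inherit the method.

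The cost is moderate. The protocol already assumes segmented charges for every patient ("All patients will have charges segmented in this manner") and already plans a crosswalk, so no new patient contact is needed. The downsides are a larger crosswalk, more ratio look-ups per hospital and year, and reliance on sites segmenting their charges similarly. Reporting both methods lets readers see how far the result depends on that last assumption.

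### Lost wages are built on the interval from surgery to a single return-to-work event, so work missed after return has no stated place in the one-year societal cost

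*Protocol*

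**What the plan says.** Section D, item 2 of the Protocol lists the components of a per-patient cost from a societal perspective. Components I and II are direct costs: the index hospitalization for all patients, and one-year all-cause hospital and professional costs for patients at sites that captured one-year utilization.

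Component III, headed Time to Return to Work, is the only indirect one. It fixes:

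- the start of the loss: "We will assume that the work halted for patients on the procedure date";
- the outcome, for patients to whom it applies: "we will compare different cohorts using return to work as a time-to-event outcome";
- the price, as a sub-item of that outcome: "Lost wages will be estimated using the median weekly earnings in the US as reported by the Bureau of Labor Statistics";
- one rule for a zero: "Patients providing no employment information will be assumed to have zero lost wages".

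Job-specific wages are ruled out. Item 2.IV then has the direct costs "combined with costs due to loss of productivity (indirect costs) to estimate total costs for each patient from a societal perspective".

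On the data side, section D, item 1.2 describes diaries at 1, 3, 6 and 12 months for all patients. "Participants were asked to monitor days missed from work and days unable to perform usual activities", and separately "days missed from work for medical treatments or evaluations". Section F, item 1 lists both the diary and the return-to-work status at those four times among the analysis variables.

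**The concern.** A weekly wage yields a cost only when multiplied by a number of weeks. The only duration that item 2.III describes opens on the procedure date and closes at return to work. A standard time-to-event outcome has one terminal event, and nothing in the item reopens the interval.

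Consider a patient who is back at work at 3 months, is re-operated at month 8 and is off work again. At a site with one-year capture, the re-operation adds direct cost under component II. The renewed absence adds nothing under component III. The same holds for single days missed for treatment or evaluation after return.

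The total in item 2.IV would then follow direct costs for a year but productivity only to the return date, and that total feeds the primary endpoint, the ventral-dorsal cost-effectiveness comparison. This is separate from how exactly the return date is known: an exact date would still leave the later loss out.

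**Working it through.** The Protocol gives no wage amount, absence rate or duration for this point, so there is no figure of its own to reproduce. The check sets the places side by side and then shows how the shortfall behaves under assumed values.

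**Step 1: what is costed and what was collected**

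| Item | Start | End | Role in the societal cost |
|---|---|---|---|
| One-year all-cause cost (D, 2.II) | surgery | 1 year | direct cost, sites with one-year capture |
| Lost wages (D, 2.III) | procedure date | return to work (the only duration given) | the only indirect cost defined |
| Diary days missed from work, and for treatment or evaluation (D, 1.2; F, 1.VIII) | surgery | 12 months | none stated for lost wages |
| Return-to-work status at 1, 3, 6 and 12 months (F, 1.VII) | 1 month | 12 months | no stated use after return |

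Re-operations and complications to 1 year are also in scope (D, item 1.1), so events that could cause a second absence fall inside the study window.

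**Step 2: share of loss missed for an affected patient**

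Let t be the weeks from surgery to return and d the weeks of later absence. True loss is t + d and costed loss is t. The share missed is d / (t + d), whatever the wage. The durations below are assumed.

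| | d = 2 | d = 6 | d = 12 |
|---|---|---|---|
| t = 6 | 2/8 = 25% | 6/12 = 50% | 12/18 = 67% |
| t = 12 | 2/14 = 14% | 6/18 = 33% | 12/24 = 50% |

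With no later absence, d = 0 and the shortfall is zero.

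**Step 3: average per employed patient in an arm**

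Let p be the share of employed patients with a later absence and w the weekly wage. The omitted mean is p × d × w. Assume w = $900; neither w nor p is in the documents.

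| | d = 2 | d = 6 | d = 12 |
|---|---|---|---|
| per affected patient, d × w | $1,800 | $5,400 | $10,800 |
| p = 5% | $90 | $270 | $540 |
| p = 10% | $180 | $540 | $1,080 |

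**Step 4: effect on the comparison**

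With the same d and w in both arms, the error in the cost difference per employed patient is (p₁ − p₂) × d × w. If p is equal in the arms, the error is zero. If p differs by 5 points with d = 6, it is 0.05 × 6 × $900 = $270. Per patient in the arm, employed or not, each figure is multiplied by the employed share, which is not given, and so is smaller. The documents contain no rate of later absence or re-operation by arm, so neither the sign nor the size of this error can be derived.

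**The case against.** The strongest reply is that the Protocol never writes the costing rule. The sentence on time-to-event describes a comparison of cohorts, not a wage formula. The wage sub-item gives a price and no duration. The event is not defined as first or sustained return. The diary is listed among the analysis variables, section D, item 1.1 says that health resource information will be used, and item 2.IV speaks of "costs due to loss of productivity (indirect costs) to estimate total costs for each patient from a societal perspective" without limiting it to time to return. Event definition and duration are commonly left to a statistical analysis plan, which is not at hand.

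Much of this stands. A reader might infer that the Protocol orders the loss to end at the first return and values every later day at zero. It does neither in words: the only explicit zero is for patients without employment information, and silence about diary days is not a rule that excludes them.

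A reader might also infer that the omission favours one approach. No place in the document gives later absence by arm or says that it is expected to differ, and the Background reports similar effectiveness for the anterior and posterior approaches.

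What does not stand is the view that the matter was simply left open. Item 2.III fixes the start date, the type of outcome, the wage source, a zero rule and the exclusion of job-specific wages, all under a heading that names time to return. Listing the diary as a variable gives it no role in wages, since its use for direct costs would explain the listing. Surgery to return remains the natural reading, and a better measure was collected.

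**Conclusion.** The point holds as a weakness in the chosen measure. Read naturally, item 2.III builds the only productivity cost on surgery to a single return, and work missed after return has no stated place in a total that is called societal and that follows direct costs to one year. Productivity loss is understated for every patient with later absence. With the assumed durations above, the share missed for such a patient runs from 14% to 67%.

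Bias between approaches is conditional on later absence differing by arm, which the documents do not show. The dollar figures rest wholly on assumed rates, durations and wage; they show scale and are not estimates. The change is worth making because the data are already listed and the present wording gives no reason to prefer the narrower measure.

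**What to change.** In item 2.III, keep time to return to work as the between-cohort outcome and separate it from the costing. Define lost wages as the total work time lost from surgery to 12 months, priced at the same weekly wage:

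- the initial absence from the procedure date to return; plus
- diary days missed from work after return, including those for treatment or evaluation.

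Count each calendar day once, because the initial absence and the two diary items can overlap. State how days are converted to weeks. Use the work status at 1, 3, 6 and 12 months only where diary days are missing, since four visits cannot date a later spell. Report a sensitivity analysis with lost wages based on time to return alone.

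The cost is analysis wording and programming, including the rule against double counting. No new collection is needed, as section F, item 1 already lists the diary and the status. The small downside is reliance on diary completeness after return: the Protocol says that participants were asked to monitor these days, not that the records are complete, and gaps cannot be filled in a post hoc analysis of deidentified data. The sensitivity analysis shows how much the result depends on those diary days.

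### Patients whose work status is unknown are assigned zero lost wages, which understates societal cost if any of them worked and can bias the ventral-dorsal cost difference

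*Protocol*

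**What the plan says.** Three statements in the Protocol have to be read together.

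- D. Research Plan, item 2.III, limits the return-to-work component to a subset: it is "performed on all patients reporting employment". Time off is counted from surgery ("We will assume that the work halted for patients on the procedure date") and valued at a national figure ("Lost wages will be estimated using the median weekly earnings in the US as reported by the Bureau of Labor Statistics"). For the remaining patients the rule is: "Patients providing no employment information will be assumed to have zero lost wages".
- Item 2.IV then adds hospital costs and "costs due to loss of productivity (indirect costs) to estimate total costs for each patient from a societal perspective". The opening of item 2 takes the same per-patient view: "The overall cost will be estimated for each patient from a societal perspective".
- F. Timepoints of Data Collection, item 2.I: "The primary endpoint will be the cost-effectiveness comparison between ventral and dorsal surgery in CSM".

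The Protocol gives no reason for choosing zero, does not separate patients known not to work from patients of unknown status, and gives no missing share, employment rate, wage amount or expected time off work.

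**The concern.** There are three kinds of patient: those who report a job, those who report having none, and those who report nothing. A retired or unemployed patient who says so has supplied employment information. Taken literally, then, the zero rule applies to the third group, the one for which zero has no stated basis. Lost wages cannot be negative, so the value filled in is the lowest possible and any error in an arm's mean is downward.

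The total cost must exist for every patient, so the filled zeros pass directly into the primary comparison. If non-response differs between arms, the arm with more unknowns looks cheaper for a reason unrelated to surgery. If non-response is equal, part of any real productivity difference disappears. The zeros also enter the variance as if observed, so the uncertainty from not knowing is lost.

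**Working it through.** The Protocol has no figure of its own to reproduce here. The bias is derived first, then illustrated with assumed values.

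**Notation.** m = share with unknown status in an arm; p = share of those who in fact worked; L = mean weeks lost if working; W = weekly wage. True mean loss among the unknowns is mu = p × L × W.

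**Bias**

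- Arm mean: changes by −m × mu = −m × p × L × W.
- Ventral minus dorsal: changes by −(m_v p_v L_v − m_d p_d L_d) × W. This is zero only if m × p × L is the same in both arms.
- Equal m, with unknowns like the observed patients: a true difference is multiplied by (1 − m).
- If p = 0, there is no bias.

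**Assumed inputs (none from the Protocol).** W = $900; L = 12 weeks (range 6 to 26); m = 20% (10% to 30%); p = 45% (30% to 60%); SD of weeks lost among workers 8.

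**Understatement of mean cost**

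- Central: 0.20 × 0.45 × 12 × 900 = $972
- Low: 0.10 × 0.30 × 6 × 900 = $162
- High: 0.30 × 0.60 × 26 × 900 = $4,212

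**False difference from a 10-point arm gap in m, equal true loss**

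- Central: 0.10 × 0.45 × 12 × 900 = $486
- Low: 0.10 × 0.30 × 6 × 900 = $162
- High: 0.10 × 0.60 × 26 × 900 = $1,404

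**Shrinkage with equal m = 20%.** A true 4-week difference among workers is worth 0.45 × 4 × 900 = $1,620 per patient. It shows as 1,620 × 0.80 = $1,296, so $324 is lost.

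**Both effects together, in weeks of earnings.** Take p = 0.5, true loss of 6 weeks (ventral) and 10 weeks (dorsal), and 10% and 20% unknown. The true difference is 3.0 − 5.0 = −2.0 weeks. The rule gives 0.90 × 3.0 − 0.80 × 5.0 = 2.7 − 4.0 = −1.3 weeks.

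**Apparent precision.** Compare the standard error of mean lost wages after zero-filling (n patients) with that from known-status patients only (n(1 − m) patients). Among workers the mean square is 12² + 8² = 208. With q = p(1 − m):

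ratio = √(208q − (12q)²) / √[(208p − (12p)²)/(1 − m)]

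| m | ratio |
|---|---|
| 0.10 | 0.920 |
| 0.20 | 0.835 |
| 0.30 | 0.746 |

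At m = 0.20: √56.22 / √80.55 = 0.835. The standard error is about 16% smaller than the known data support (8% to 25% over the range).

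**The case against.** The best counter-argument is about meaning. The rule sits under a heading limited to patients with a job, so it could be read as covering everyone else: no job, no lost wages. On that reading nothing is biased and only the wording is loose. But the rule speaks of patients who provide no information, not of patients who do not work. An analyst following it would assign zero to the unknowns.

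Second, the affected group may be small. Section F lists baseline demographics, return-to-work status at four visits and a diary at four time points, and a patient blank on all of these may be rare or mostly not working. This stands as a limit on size: the 10% to 30% range is an assumption, and the effect has not been set against total cost or its variance.

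Third, nothing in the Protocol suggests non-response differs by arm, and in a randomised trial employment recorded before surgery would be missing unequally only by chance. That is fair for baseline data. Return-to-work status and diaries, however, are collected from 1 month to 1 year after surgery, when response can depend on approach and recovery. Equal missingness still shrinks a real difference.

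Fourth, the precision point is modest. At 20% unknown, the difference falls to 0.80 and its standard error to 0.835 of the known-status value, so their ratio falls only about 4% (0.80/0.835 = 0.958). This also stands, and the 16% figure concerns lost wages alone, not total cost.

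Finally, missing-data methods are normally left to a statistical analysis plan. Here, though, the Protocol itself fixes a specific, one-directional rule, and that rule is what is at issue.

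**Conclusion.** The concern holds. As written, the Protocol treats unknown work status as no loss and feeds that value into the total behind its primary endpoint. Each arm's cost is understated if any non-reporter worked and lost time. The arm difference is correct only if the understatement happens to be equal in both arms.

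The algebra does not depend on the assumed inputs, but the dollar amounts do. Neither the size nor the direction of the bias in the ventral-dorsal difference can be determined from the Protocol, and if non-reporters are few or nearly all out of work the effect is small. This should be corrected before analysis; it does not by itself invalidate the comparison.

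**What to change.** Replace the rule in item 2.III with wording such as:

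> Lost wages are zero only for patients recorded as not working (for example retired or unemployed). Patients with no employment information are treated as missing; employment and weeks lost are multiply imputed by arm from baseline demographics, site and baseline scores, together with any return-to-work and diary data available.

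Report the number with unknown work status by arm, and keep the zero rule as a sensitivity analysis so that its influence is visible. If the rule was meant only for patients reported as not working, the new first sentence says so, and the imputation will matter little.

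The cost is one changed rule and modest extra analysis, with no new data collection. Baseline demographics, scores, return-to-work status and the diary are listed in section F; site is not listed as a variable but is implied by the hospital-specific cost-to-charge ratios. Some unknowns may be resolved directly from the diary or visit data before imputation. The drawbacks are somewhat wider intervals and reliance on a missing-at-random assumption that cannot be verified. The present rule relies on the stronger, unstated assumption that every patient of unknown status lost nothing.
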